1 Safety Run-in	A	Ad-RTS-hIL-12 monotherapy; n=6 [INXN-1001 (140 mg daily) + INXN-2001 (███████████)]
	C	Combination therapy; n=3 [INXN-1001 (140 mg daily) + INXN-2001 ██████████ ██████████ + palifosfamide (120 mg/m ²)]
2 Randomization	A	Ad-RTS-hIL-12 monotherapy [INXN-1001 (140 mg daily) + INXN-2001 ██████████ 10 ¹² vp)]
	C	Combination therapy [INXN-1001 (140 mg daily) + INXN-2001 ██████████ ██████████ + palifosfamide (120 mg/m ²)]

	
treatment, then this treatment arm will be included in Part 2 of the study.
 
During Part 2, 9 additional subjects will be randomly assigned to Arm C. If <6 of the first 12 (3+9) subjects survive progression-free at week 16, no additional subjects will be enrolled. If ≥ 6 of the 12 subjects survive progression-free at week 16, an additional 14 subjects will be randomly assigned. If ≥ 15 of the 26 (3 + 9 + 14) subjects in the expansion cohort survive progression-free at week 16, then this regimen would be considered worthy of further investigation (ie, a confirmatory trial).
 
The primary efficacy endpoint is the 16-week PFS rate, defined as the proportion of subjects that remain progression-free at week 16 by mRECIST v1.1 for Arms A and C. Futility decisions will be made using results at week 16 from both primary and secondary endpoints.
 
The safety of study treatments will be assessed throughout the study by the frequency and severity of adverse events (AEs) as determined by the National Cancer Institute (NCI) Common Terminology Criteria for Adverse Events (CTCAE) v4.03.
 
An SRC meeting can be convened if deemed necessary by the sponsor or the investigators at any point during the study.

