Statistical Considerations / Analyses	
This study is designed to evaluate the safety and efficacy of Ad-RTS-hIL-12 monotherapy or in combination with palifosfamide as determined by the 16-week PFS rate, defined as the proportion of subjects that survive progression-free at week 16.
 
Statistical analysis will be performed separately for each study arm. Demographics and baseline characteristics will be summarized by treatment regimen.
 
Primary Endpoints:
 
• Safety and tolerability of therapy• 16-week PFS rate 
Secondary Endpoints:
 
• Estimated PFS, duration of response, ORR, CBR 
Sample Size:
 
The study will have 2 study arms and include a safety run-in as Part 1. Part 2 will have 2 study arms and utilize an adaptive Simon 2-stage design. Progressive disease will be assessed by mRECIST v1.1 at week 12, week 16, and at the Follow-up Tumor Assessment (week 24).
 
Treatment Arm A: Ad-RTS-hIL-12 Monotherapy
 
Part 1 will explore the safety Ad-RTS-hIL-12 monotherapy in 6 subjects, after 1 Cycle of therapy. During Part 2 for efficacy assessments, assume a targeted proportion of subjects who survive progression-free at week 16 of 35% with a proportion of no interest of 15%.
 
a) Stage 1: if ≥ 1 subject of the first 6 subjects survives progression-free at week 16, add 7 subjects (n=13) to complete Stage 1b) Stage 2: if ≥ 3 of 13 subjects survive progression-free at week 16 in Stage 1, add 20 subjects (n=33) to complete Stage 2c) Possible Confirmatory Trial: if ≥ 9 of the total of 33 subjects survive progression-free at week 16, consider confirmatory trial

	
Treatment Arm C: Combination Therapy
 
Part 1 will explore the safety of combination therapy in 3 subjects after 1 cycle of therapy.
 
During Part 2 for efficacy assessments, assume a targeted proportion of subjects who survive progression-free at week 16 of 65% with a proportion of no interest of 40%.
 
a) Stage 1: add 9 subjects (n=12) to complete Stage 1b) Stage 2: if ≥ 6 of 12 subjects survive progression-free at week 16 in Stage 1, add 14 subjects (n=26) to complete Stage 2c) Possible Confirmatory Trial: if ≥ 15 of the total of 26 subjects survive progression-free at week 16, consider confirmatory trial 
The tumor responses will be assessed by mRECIST v1.1.

--	--

SCHEDULE OF STUDY PROCEDURES AND ASSESSMENTS

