3.5 Rationale for Study Design and Dose Selection

The objectives of this Phase II clinical trial are to assess the safety and tolerability, PFS rate at 16 weeks, ORR, and immunological and biological effects of IT injections of INXN-2001 + INXN-1001 as monotherapy or in combination with palifosfamide. To provide an opportunity to monitor the safety of Ad-RTS-hIL-12 monotherapy and Ad-RTS-hIL-12 + palifosfamide (combination therapy) in subjects with breast cancer, a safety run-in will occur, with evaluation following one cycle of study drug.

The study will commence with Ad-RTS-hIL-12 monotherapy using a 140-mg dose of INXN-1001 administered daily Days 1-7 in 6 subjects (21-day cycle). Following a safety assessment, combination therapy of Ad-RTS-hIL-12 + palifosfamide (120 mg/m², Days 1, 2, 3 of a 21-day cycle, n=3) will commence. Safety in Part 1 of the study will determine commencement of randomization for Part 2.

During the conduct of this study, in addition to monitoring of safety and therapeutic efficacy, peripheral blood samples will be studied for indications of immunological and biological effects including analyses of breast cancer-associated cytokines/biomarkers. The combined clinical and laboratory data will be studied to assess for activity, and will be used in decision making for expansion of treatment arms.

The population for this study was selected as those subjects with recurrent or metastatic breast cancer (which is rarely curable with standard therapy) and accessible lesions, who are therefore considered to be appropriate candidates for clinical trials exploring new forms of treatment. Because breast cancers may be responsive to immunotherapeutic approaches (see [Section 4.1 Disease Background](#)), this subject population may potentially benefit from investigational therapy with Ad-RTS-hIL-12 alone or in combination with palifosfamide.

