8.1 Determination of Sample Size

In view of up to 3 novel investigational drugs being tested in this study, the sponsor has incorporated a Safety Run-in (Part 1) to evaluate safety for each study arm before fully enrolling all subjects required in Stage 1 of Part 2 for each study arm (for details please see [Section 5.1.1](#)).

The sample size of Part 2 is determined based on a Simon 2-stage design for each study arm. For Ad-RTS-hIL-12 monotherapy (Arm A) with 13 subjects evaluated in Stage 1 and an additional 20 subjects in Stage 2 if applicable, it will provide 80% power at 1-sided 5% significance level to differentiate 35% targeted proportion of subjects who survive progression-free at week 16 from a proportion of no interest of 15%. If ≥ 3 of 13 subjects survived progression-free at week 16 in Stage 1, 20 additional subjects will be evaluated in Stage 2.

For the Ad-RTS-hIL-12 + palifosfamide combination (Arm C), with 12 subjects evaluated in Stage 1 and an additional 14 subjects evaluated in Stage 2, it will provide 80% power at 1-sided 5% significance level to differentiate 65% targeted proportion of subjects who survive progression-free at week 16 from a proportion of no interest of 40%. If ≥ 6 of 12 subjects survived progression-free at week 16 in Stage 1, 14 additional subjects will be evaluated in Stage 2.

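### The Protocol lets secondary endpoints and laboratory data into the Stage 1 decision, but its 80% power is derived from a gate that uses the 16-week count alone

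*Protocol*

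**What the plan says.** Two bases for the Stage 1 decision stand in the current Protocol.

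**Count only.**
- The Study Design part of the Synopsis introduces the futility analyses as resting on PFS at week 16. For Arm C it says that if fewer than 6 of the first 12 "subjects survive progression-free at week 16, no additional subjects will be enrolled".
- The Synopsis sample-size text gives the gates and final cut-offs. Arm A needs at least 1 of 6, then 3 of 13, then 9 of 33. Arm C needs at least 6 of 12, then 15 of 26.
- Section 8.1 repeats the main gates. For Arm A, if at least 3 of 13 "subjects survived progression-free at week 16 in Stage 1, 20 additional subjects will be evaluated in Stage 2". It derives the power from them: "it will provide 80% power at 1-sided 5% significance level to differentiate 35% targeted proportion".
- Section 4.1.5 refers futility criteria to the statistics section and says expansion follows a Simon two-stage scheme.

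**Count plus other data.**
- The Synopsis also says "Futility decisions will be made using results at week 16 from both primary and secondary endpoints".
- Section 3.5 says the combined clinical and laboratory data "will be used in decision making for expansion of treatment arms".

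No section gives a threshold, weight or order of precedence for the secondary or laboratory data, or says whether they can override the count. The supplied SAP describes a single-arm study with 12-week endpoints (SAP Sections 5.2 and 10.1) and has no futility rule, so it does not settle the matter.

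**The concern.** Power is a property of the rule that is actually applied. Section 8.1 computes it for a rule with one input, the 16-week count. If response rate, clinical benefit rate or biomarkers can also end an arm, the rule has further inputs that nobody has specified, and 80% no longer describes it. The trial is open-label, so these data will be visible when the decision is taken. The practical risk is that an active arm is dropped more often than the plan states. If the extra data were instead used to carry on an arm that missed its count, 20 (Arm A) or 14 (Arm C) more subjects would enter an arm that the written rule would close.

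**Working it through.** **Inputs** (Protocol Synopsis and Section 8.1)
- Arm A: n1 = 13, gate c1 = 3, n2 = 20, final cut-off c = 9 of 33, p0 = 0.15, p1 = 0.35.
- Arm C: n1 = 12, c1 = 6, n2 = 14, c = 15 of 26, p0 = 0.40, p1 = 0.65.

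**Step 1: reproduce the plan's figures.** For the count-only rule,

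P(success | p) = Σ over x from c1 to n1 of Bin(x; n1, p) × P(Bin(n2, p) ≥ c − x).

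| | At p0 (type I error) | At p1 (power) |
|---|---|---|
| Arm A | 4.12% | 80.84% |
| Arm C | 4.69% | 80.86% |

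The stated 80% and one-sided 5% (read as a ceiling) are reproduced. The margin over 80% is under one percentage point in each arm.

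**Step 2: Arm A's additional look.** The figure above leaves out the Synopsis requirement of at least 1 progression-free subject among the first 6. Let a be the count in the first 6 and d the count in the next 7. Summing over a ≥ 1 and a + d ≥ 3 gives power 77.95% and type I error 3.88%. The full Arm A count rule is therefore already about two points short of 80%. Steps 3 and 4 use the two-stage rule without this look, as Section 8.1 does.

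**Step 3: other data stop an arm that met its count.** The Protocol gives no rule, so both versions below are assumptions.

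(a) An extra stop with probability q, independent of the counts, gives power = count-rule power × (1 − q). With q = 10%, 0.8084 × 0.90 = 72.8% (Arm A) and 0.8086 × 0.90 = 72.8% (Arm C). With q = 20%, both are 64.7%. Power drops below 80% once q exceeds 1 − 0.80/0.8084 = 1.04% (Arm A) or 1 − 0.80/0.8086 = 1.06% (Arm C).

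(b) At least 1 responder is also required in Stage 1, with responders a subset of the progression-free subjects. Each term of the Step 1 sum is multiplied by 1 − (1 − ORR/p1)^x:

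| True ORR | Arm A power | Arm C power |
|---|---|---|
| 10% | 64.3% | 60.0% |
| 20% | 78.8% | 76.5% |
| 30% | 80.8% | 80.2% |

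The loss is large when responses are rare and almost nil at 30%.

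**Step 4: other data carry on an arm that missed its count.** Success still needs 9 of 33 or 15 of 26. Whatever the Stage 1 rule, the chance of success therefore cannot exceed P(Bin(N, p) ≥ c), the value with no gate at all:
- Arm A: P(Bin(33, 0.15) ≥ 9) = 4.95%.
- Arm C: P(Bin(26, 0.40) ≥ 15) = 5.18%.

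What does change is how often an arm at the no-interest rate goes on. If arms one short of the gate are continued (again an assumption), this rises from 30.8% to 60.2% in Arm A and from 33.5% to 56.2% in Arm C.

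**The case against.** The best defence is that the Protocol already shows which text governs. Section 4.1.5, the operative expansion section, points to the statistics section and a Simon scheme, and Section 8.1 uses counts only. Section 3.5 is a rationale section, and data used in decision-making can support a count gate without displacing it. On that view this is a stray sentence, and an exploratory open-label phase II trial may reasonably keep some judgement. The magnitudes also rest on override rules that appear nowhere in the documents.

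Much of this stands. The documents lean towards the count rule, and the power figures are illustrations. It does not remove the conflict, because the Synopsis says futility decisions will be made using both kinds of endpoint, which is stronger than calling the secondary ones supportive. Confirmed response is also an awkward input at that time. Section 8.4.2 asks for confirmation at least 28 days later, while the two scans by week 16 fall on C5D1 (4 × 21 + 1 = day 85) and C6D7 (5 × 21 + 7 = day 112), 27 days apart.

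Two stronger readings are tempting. A reader might infer that the 5% error rate is lost as well. It is not: extra stopping can only lower it, and Step 4 caps it. A reader might also infer that the text permits rescue of a failed arm. The Synopsis sentence is about futility, and rescue would contradict the explicit Arm C stop in the same section. Only the looser Section 3.5 clause leaves room for it.

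**Conclusion.** The inconsistency is real and worth correcting. It affects power, not the error rate in any material way. As written, power is undetermined. It stays near 80% if the extra data seldom stop an arm that met its count, and could be 60% to 65% under a plausible but assumed one-responder requirement with a 10% response rate. Type I error is at most 4.95% in Arm A, under the 5% ceiling, and at most 5.18% in Arm C, an excess of no more than 0.18 points. That cap assumes that the sample sizes and final cut-offs stay fixed; the effect of subject replacement under Section 5.4 was not examined. The main cost of continuing an arm that missed its count is further enrolment in an arm the rule would close. Independently of the wording conflict, Arm A's stated 80% does not allow for the look at 6 subjects; with it, power is 77.95%.

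**What to change.** Amend the Synopsis futility sentence and the Section 3.5 clause to say that efficacy futility and expansion follow the 16-week progression-free counts in the Synopsis sample-size text and Section 8.1. Secondary endpoints and biomarkers would be reported at the gate as supportive information only. State that safety stops by the Safety Review Committee or the sponsor are unaffected. If the sponsor wants an additional efficacy criterion, define it, say whether it is binding and in which direction, and restate power under it. In the same edit, give Arm A's power with the look at 6 subjects included.

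The cost is two reworded passages and one restated figure. The downside is that the sponsor gives up some discretion at the gate.

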7. Monitoring and recording of adverse events (AEs) and serious adverse events (SAEs) will be conducted throughout the study. AEs/SAEs that occur following informed consent until the Post-Treatment Safety Assessment must be recorded on the AE case report form (CRF); AEs/SAEs that occur prior to informed consent should be added to the medical history CRF.
In addition, all SAEs must be reported by the investigator or designee within 24 hours of becoming aware of the event, from the time of informed consent through 30 days after the last dose of study drug, regardless of the initiation of any new anticancer therapy.
8. Concomitant medication information, including blood products, vitamins, and other supplements will be collected for the time period beginning 28 days prior to the first dose of study drug, through the Follow-Up Tumor Assessment visit.
9. Females of childbearing potential will have a serum pregnancy test at the Screening visit and a urine or serum pregnancy test on the first day of each treatment cycle, prior to administration of any study drug.
10. Hematology tests include: complete blood count (CBC) and white blood cell (WBC) count, differential white blood cell count, red blood cell (RBC) count, hematocrit, hemoglobin, red blood cell indices, reticulocyte count, MCV (mean corpuscular volume) and platelet count. PTT (partial thromboplastin time) and INR (international normalized ratio) will also be evaluated.
11. Serum chemistry tests include: aspartate transaminase (AST), alanine transaminase (ALT), lactate dehydrogenase (LDH), alkaline phosphatase (ALP), creatinine (eGFR), total bilirubin, total protein, albumin, blood urea nitrogen (BUN), glucose, sodium, potassium, chloride, calcium, phosphorus, and bicarbonate.

12. Urinalysis panel (dipstick) includes: appearance, pH, specific gravity, glucose, protein/albumin, blood, ketones, bilirubin, nitrates, and leukocyte esterase. In addition, a microscopic exam for casts, crystals, and cells may be done if clinically indicated.
13. Standard, single 12-lead ECG at screening, and prior to dosing of INXN-1001 and/or INXN-2001 injection and/or palifosfamide infusion on Day 1 of each cycle, and at the Post-Treatment Safety Assessment visit.

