17. Digital photograph(s) of all visible injected and non-injected tumor(s), and of any visible local reactions in or around the injected lesion(s). Photographs are required post-registration, Cycle 2 Day 7, Cycle 5 Day 1, Cycle 6 Day 7, Post-Treatment Safety Assessment, and Follow-Up Treatment Assessment visits, and ad hoc as the investigator deems necessary. Important guidelines regarding photographic methodology will be provided in a separate manual.
18. Intratumoral INXN-2001 [REDACTED] injection should be administered 3 hours \pm 30 minutes after the INXN-1001 dose. [REDACTED]
[REDACTED] Each subject will be carefully monitored for possible local reactions at the injection site and/or hypersensitivity reactions for at least 2 hours following the INXN-2001 injection. A detailed description of physical location(s) of the injected tumor(s) and surrounding tissue, and any visible local reactions will be documented. The [REDACTED]

19. The subjects will be dispensed INXN-1001 for self-administration after Day 1. The first INXN-1001 dose will be given at the clinical site in a fed state (within approximately 30 minutes after the start of a normal meal). The remaining 6 doses can be self-administered at the same time as on Day 1 (\pm 1 hour) in the fed state. Study sites must verify adherence with INXN-1001 dosing. Subjects should return bottles of INXN-1001 to the clinical site to determine extent of subject adherence to self-administration preferably on Day 7.
20. The following temporal sequences of drug administration for Arm A monotherapy and Arm C combination therapy will be followed:

For subjects enrolled in Arm C Ad-RTS-hIL-12 + palifosfamide Combination Therapy, the sequences for monotherapy + palifosfamide (sequences for Arms A + C) will be followed concurrently as shown above.

21. Day 1 clinical laboratory assessments may be performed within 15 days of the previous cycle through the Day 1 (prior to dosing) clinic visit. Clinical laboratory tests drawn for analysis prior to dosing on Day 15 of each cycle may be used for determining if the re-treatment criteria have been met, and must be reviewed by the investigator or designee prior to the next cycle of study drug administration. Repeat assessments may be obtained for those subjects with parameters \geq Grade 3.

- 22. Post-Treatment Safety Assessment visit will be performed 28 ± 3 days after the last dose of study drug or prior to receiving another anticancer therapy.

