7.3 Documenting Adverse Events (AEs)

All AEs (including SAEs) are to be accurately recorded on the Adverse Event page of the subject's electronic CRF from the time the subject signs the informed consent until the Post-Treatment Safety visit. Each event will be assessed for serious criteria, severity, and causality (see "Causality Assessments"). The date of onset, as well as the duration of the event will be recorded. In addition, treatments provided to the subject, actions taken with the study drugs, and the outcome of the AE will also be noted.

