7.4 Reporting Serious Adverse Events (SAEs)

Time Frame for Reporting

SAEs must be reported to the Sponsor or Sponsor's designee (within 24 hours) of becoming aware of the event (regardless of the initiation of any new anticancer therapy) including the following:

- Any death or SAE experienced by the subject from the signing of informed consent to 30 days after the last dose of study drug, regardless of relationship to study drug.
- Any death or SAE that the Investigator becomes aware of, and believes to be study drug related, that occurs more than 30 days after the subject last received study drug.

Study drug-related AEs/SAEs that are ongoing at the time of the Post-Treatment Safety Assessment visit should continue to be followed until resolution, return to baseline, or until they have stabilized or become chronic (and following consultation and agreement by the ZIOPHARM Medical Monitor).

Information to be provided by the Investigator

Within 24 hours of becoming aware of the SAE or subject death, the investigator must notify the Sponsor or designee and transmit information to the Sponsor or designee. Information (initial and follow-up) should be provided on an electronic and/or paper SAE Report form signed and dated by the investigator. The SAE Report form and copies of source documents (with subject identifiers redacted) will be transmitted by fax. A hospital discharge summary should be provided if the subject was hospitalized. An SAE report will be considered final once all relevant information has been received and reviewed by the Sponsor.

The SAE Report form is provided in the investigator study files. Please refer to the investigator study files for instructions on how to complete the form. The investigator will provide all of the following information related to the event:

- Investigator identification
- Subject identification (e.g., subject number, initials, sex, age or date of birth)
- Information regarding study drug administration (e.g., start/stop date, dose, and frequency)
- Description of event
- Action taken with the study drugs in relation to the SAE
- Outcome of the SAE

In addition to the above information, the investigator must provide, for each event term, an assessment of:

- Severity/intensity
- Relationship to the study drug (causality assessment)

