8. STATISTICAL PROCEDURES

Data from this study will be analyzed and included in a clinical study report that will be prepared after the last subject has completed the Post-Treatment Safety Assessment visit. Additional data collected from subjects who have not progressed by the Follow-Up Tumor Assessment visit and are continuing to be followed for tumor response at the time of the final data cut-off date will be presented in an addendum to the study report.

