8.4.4 Safety Endpoints

The safety endpoints will include AEs, vital signs, ECG, physical examinations, laboratory data, and concomitant medications. All AEs will be coded according to Medical Dictionary

for Regulatory Activities (MedDRA®, version 13.0 or later). Concomitant medications will be coded using the World Health Organization Drug Dictionary, September 2006 or later.

The incidence, onset timing, duration, severity, relationship, and outcome will be listed for each AE. All treatment-emergent AEs (TEAEs) occurring on-study will be analyzed by treatment group and listed in by-subject data listings. Events that are considered related to treatment (possibly related or related) will also be tabulated.

Treatment-emergent AEs will be tabulated overall and by subject. ‘Treatment-emergent’ is defined as any AE that occurs during or after administration of the first dose of study drug through the Post-Treatment Safety Assessment visit (28 days after last dose of study drug); any event after the first dose of study drug that is considered study drug-related regardless of the start date of the event; or any event that is present at baseline that worsens in intensity or is subsequently considered to be drug related by the investigator. Serious TEAEs and related TEAEs will be summarized in a similar fashion. AEs to be presented will include TEAEs, treatment-emergent SAEs, and treatment-emergent related AEs, as well as the severity of the events. Timing relative to study treatment administration will also be presented. Treatment-related SAEs will also be summarized by treatment group and presented on a case-by-case basis in listings and narratives.

Dosing and study drug tolerability will also be assessed.

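### SAEs and deaths judged unrelated are reportable to Day 30 after last dose, but the AE case report form and the treatment-emergent window end at a visit that can come sooner

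*Protocol*

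**What the plan says.** Four provisions of the protocol bear on this point.

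- **AE form.** Footnote 7 to Tables 2A & 2B states: "AEs/SAEs that occur following informed consent until the Post-Treatment Safety Assessment must be recorded on the AE case report form". Section 6.4.2.6 repeats this. Section 7.3 gives the same window, SAEs included: "from the time the subject signs the informed consent until the Post-Treatment Safety visit".
- **Timing of the visit.** Footnote 22 says that the Post-Treatment Safety Assessment "will be performed 28 ± 3 days after the last dose of study drug or prior to receiving another anticancer therapy". The second alternative has no earliest day.
- **SAE reporting.** Footnote 7 requires SAE reports "through 30 days after the last dose of study drug, regardless of the initiation of any new anticancer therapy". Section 7.4 covers any death or SAE "from the signing of informed consent to 30 days after the last dose of study drug, regardless of relationship to study drug". Section 7.2.1.1 also uses 30 days when it defines a fatal SAE.
- **Treatment-emergent definition.** In Section 8.4.4 the time-based limb runs from first dose "through the Post-Treatment Safety Assessment visit (28 days after last dose of study drug"). A further limb keeps drug-related events treatment-emergent whenever they start, and another covers baseline events that worsen or are later judged related.

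Section 8.6.3 tabulates treatment-emergent events. It also calls for listings of deaths and SAEs, with no treatment-emergent restriction.

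**The concern.** The form and the treatment-emergent time limb share one endpoint, the visit. SAE reporting has another, Day 30, and by its own terms it does not stop at new therapy. The parenthetical 28 days in Section 8.4.4 adds to the confusion, because footnote 22 allows Day 25 to Day 31, or any earlier day before new therapy.

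Safety is a primary endpoint, and its summary tables are built on treatment-emergent events. Two features make the mismatch more than untidy.

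- The omission would not be random. The visit moves forward because a subject is about to start another therapy, so the longest gaps arise in subjects leaving study treatment for something else.
- For a late event, the investigator's causality judgement in an open-label trial decides whether it counts as treatment-emergent.

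The efficacy endpoints do not recover these deaths. In Section 8.4.2 a death counts towards PFS only if it precedes progression, and no overall survival endpoint is defined. Section 7.1 allows fatal progression to be reported as an SAE, and such an event is a natural candidate for an unrelated attribution. In arms that start with 6 and 3 subjects, one missing death would be visible.

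**Working it through.** The plan states no statistical figure to reproduce here. The check sets the windows side by side and does the day arithmetic.

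**Inputs, in days after last dose**

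| Item | Endpoint | Source |
|---|---|---|
| AE/SAE entry on the AE form | Visit day *v* | Footnote 7; Sections 6.4.2.6, 7.3 |
| Treatment-emergent time limb | Visit day *v* | Section 8.4.4 |
| Visit day *v* | 25 to 31, or earlier before new therapy | Footnote 22 |
| SAE and death reporting | Day 30 | Footnote 7; Section 7.4 |
| Related events as treatment-emergent | No end date | Section 8.4.4 |

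**Gap.** For an SAE or death judged unrelated, gap = max(0, 30 − *v*).

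| Visit day *v* | Gap (days) | Share of the 30 days |
|---|---|---|
| 31 | 0 | 0% |
| 30 | 0 | 0% |
| 28 | 30 − 28 = 2 | 2/30 = 6.7% |
| 25 | 30 − 25 = 5 | 5/30 = 16.7% |
| 21 (brought forward) | 30 − 21 = 9 | 9/30 = 30.0% |
| 14 (brought forward) | 30 − 14 = 16 | 16/30 = 53.3% |
| 7 (brought forward) | 30 − 7 = 23 | 23/30 = 76.7% |

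**Worked case.** Suppose the visit is on Day 7, another drug starts on Day 8, and the subject dies on Day 20 of a cause judged unrelated.

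1. 20 ≤ 30, so the death must be reported.
2. 20 > 7, so it is not due on the AE form.
3. 20 > 7 and it is unrelated, so it meets neither the time limb nor the related-event limb, and is not treatment-emergent.

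**Illustration of size, on assumed risks.** The documents give no event risk. Assume a 5% to 20% chance per subject of an unrelated SAE or death in the 30 days after last dose, spread evenly, with every visit on the same day. Expected events outside the time limb = N × risk × gap/30.

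| Visit day for all subjects | N = 62 | N = 9 |
|---|---|---|
| 28 | 62 × 0.05 × 2/30 = 0.21, to 62 × 0.20 × 2/30 = 0.83 | 0.03 to 0.12 |
| 25 | 62 × 0.05 × 5/30 = 0.52, to 62 × 0.20 × 5/30 = 2.07 | 0.075 to 0.30 |
| 14 | 62 × 0.05 × 16/30 = 1.65, to 62 × 0.20 × 16/30 = 6.61 | 0.24 to 0.96 |

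The Day 14 row treats every visit as brought forward, so it is an extreme and not a forecast.

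**SAP.** Section 9.2 of the SAP ends the treatment-emergent period 6 weeks after first dose. Its Section 5.2 describes a single-arm, single-center, one-cycle study. Six weeks is 42 days, or 42/21 = 2 of the protocol's 6 cycles. The SAP therefore does not settle the question and adds a third endpoint.

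**The case against.** The case on the other side has real force.

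- **Related events are safe by definition.** A reader might infer that the treatment-emergent definition shuts at the visit for all events. It does not, since Section 8.4.4 keeps related events whatever their start date. This stands, and confines the definitional gap to events judged unrelated.
- **Listings are not restricted.** A reader might infer that late deaths vanish from the report. Section 8.6.3 calls for deaths and SAEs to be listed without a treatment-emergent limit, so no stated rule removes them. This stands for listings. However, Section 7.4 sends SAE forms to the sponsor separately, and nothing says how they are reconciled with the case report form data. That leaves the source of the listings open, and the handling of a late related SAE too.
- **A duty to record until the visit does not forbid later entry.** Footnote 7 does open by saying that monitoring and recording continue throughout the study. But its next sentence sets the endpoint for the form, and Sections 6.4.2.6 and 7.3 repeat it.
- **Stopping at new therapy limits confounding by that therapy.** This is a reasonable choice for non-serious AEs. It is weaker for SAEs and deaths, which the protocol already requires past that point; a flag deals with the confounding.
- **The report could be cut too early.** This inference is tempting because Section 8 has the report "prepared after the last subject has completed the Post-Treatment Safety Assessment visit". That wording sets a lower bound, not a cut. The same section names a separate final data cut-off at which subjects not progressed by the Follow-Up Tumor Assessment are still being followed. That assessment is 35 ± 7 days after the safety visit, so at the earliest Day 25 + 28 = 53, or Day 7 + 28 = 35 for a Day 7 visit. Both are past Day 30, and the documents do not support the inference.

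**Conclusion.** The mismatch is in the text and should be corrected. An SAE or death judged unrelated, occurring after the Post-Treatment Safety Assessment and by Day 30 after last dose, is reportable but is neither due on the AE form nor treatment-emergent. It can therefore be absent from the treatment-emergent SAE tables that support a primary endpoint.

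For a visit on schedule the gap is at most 5 days, 2 at the nominal Day 28, and none at Day 30 or 31. It lengthens only when the visit is brought forward for new therapy. How often that happens is not given, and the number of events may be small.

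A reader might take the design rates for week 16 as evidence that early change of therapy will be common, since they imply that many subjects will not be progression-free. The documents do not support that step. Those rates are planning hypotheses, a missing week 16 assessment also counts as not progression-free (Section 8.4.1), and subjects with progression may still complete 6 cycles (Section 4.1.2).

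The conclusion assumes that sites follow the form window as written and that no reconciliation procedure exists outside these documents.

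**What to change.** 1. Keep collection on the AE form from informed consent, so that events before the first dose are not lost. For all SAEs and deaths, extend it to the later of the visit and Day 30 after last dose, regardless of new anticancer therapy. Using the later date also protects events before a permitted Day 31 visit. Amend footnote 7 and Sections 6.4.2.6 and 7.3.
2. In Section 8.4.4, tabulate these SAEs and deaths by arm over the same window, flagged as before or after the start of new anticancer therapy. Keep the related-event limb as it is.
3. Replace the parenthetical 28 days in Section 8.4.4 with wording that matches footnote 22.
4. State that SAE reports are reconciled with the case report form data before the tables and listings are run.
5. Align the treatment-emergent window in SAP Section 9.2 with the protocol.

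The cost is wording in these sections, one flag in the AE dataset and the reconciliation step. The SAE and death data are already required by Section 7.4, and non-serious AEs need no longer window. Tabulated SAE and death counts may rise slightly, with the flag showing which events followed other therapy.
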